# 4.4 Patients of Reproductive Potential

The patient must not be pregnant or breast-feeding at inclusion in the study. Absence of pregnancy must be demonstrated by urine testing unless there is proven menopause (age  $\geq 50$  years and last menarche  $\geq 3$  years, or documented menopausal sex hormone profile, or surgical castration) prior to exposure to the investigational product or any study procedure with potential risk to the fetus.

Female patients must not become pregnant or start breast-feeding during the study, and women of childbearing potential (i.e. without proven menopause, see above) must use a medically effective contraception during the study and within 6 months after the last study medication intake, as must male patients with a sexual partner of childbearing potential.

#### 5 STUDY TREATMENT

#### 5.1 Formulation and Manufacturer

Drug code	OTX015/MK-8628 (investigational agent)
INN	Not yet issued
Formulation	OTX015/MK-8628 is provided in gelatin capsules as a solid molecular dispersion as follows:
	10 mg capsules (white, size 3): OTX015/MK-8628 free base (10 mg), hypromellose acetate succinate (HPMCAS; 10 mg), lactose monohydrate (85 mg), microcrystalline cellulose (70 mg), croscarmellose sodium (10 mg), colloidal silicon dioxide (2.5 mg), and magnesium stearate excipients (2.5 mg).
	20 mg capsules (green, size 3): OTX015/MK-8628 free base (20 mg), HPMCAS (20 mg), lactose monohydrate (74 mg), microcrystalline cellulose (61 mg), croscarmellose sodium (10 mg), colloidal silicon dioxide (2.5 mg), and magnesium stearate excipients (2.5 mg).
	40 mg capsules (white, size 0): OTX015/MK-8628 free base (40 mg), HPMCAS (40 mg), lactose monohydrate (196 mg), microcrystalline cellulose (162 mg), croscarmellose sodium (25 mg), colloidal silicon dioxide (6 mg), and magnesium stearate excipients (6 mg).
Storage	Capsules should be stored at +2 to +8°C (refrigerated)
Manufacturers	Agere Pharmaceuticals Inc.
	[name]
	Merck Sharp & Dohme Limited
	[name]

#### 5.2 Dosage Schedule

# 5.2.1 Prophylactic Medication Regimen

No systematic premedication will be given at least during the first cycle, however low dose prophylactic low molecular weight heparin (LMWH) is permitted throughout the study, including cycle 1.

# 5.2.2 Schedule

OTX015/MK-8628 is to be administered *per os* once daily in a fasted state with a little water just before breakfast (around 8 a.m. [±2h]). Flat doses will be used with no adjustment for BSA or weight.

Two regimens will be evaluated; OTX015/MK-8628 will be administered either continuously (Regimen 1) or for 1 week ON/2 weeks OFF (Regimen 2). Capsules must not be opened or chewed.

A treatment cycle is 21 days (3 weeks). The subsequent cycle will begin on day 22 or after recovery from any AEs associated with the previous cycle.

Patients should receive study treatment within 7 days following registration.

Dosing not performed at the same time  $(\pm 2h)$  as on other days will be omitted. Patients are to be instructed that if they vomit or omit their dose in that time frame, it is not to be replaced.

Details of the exact dose and time of administration will be documented in a patient diary and reported in the electronic case report form (eCRF).

Patients will receive OTX015/MK-8628 at the DL they were assigned at entry throughout the study, or at a reduced dose according to toxicity encountered.

\* Evaluated during the first 21 days of treatment

# **5.2.4** Dose Limiting Toxicity

DLT is defined as any of the following toxicities occurring during the first 21 days of treatment and considered by the investigator to be related to OTX015/MK-8628.

#### Hematologic toxicity

- Any grade 4 hematologic toxicity or febrile neutropenia
- Grade 3 neutropenia with infection
- Grade 3 thrombocytopenia with bleeding or lasting > 7 days

# Non-hematologic toxicity

- Any grade 3 or 4 non-hematologic toxicity (regardless of duration) unless it was not optimally
  managed with supportive care (e.g. grade 3 vomiting not adequately treated according to antiemetic
  standard of care).
- Any grade 3 or 4 laboratory abnormality, with or without symptoms, lasting > 48 hours.
- Any intolerable grade 2 non-hematologic toxicity resulting in study drug discontinuation or delay > 7 days with or without dose reduction.
- Any of the following liver test abnormalities\*\* (see Appendix 5)
  - ALT or AST  $> 8 \times ULN$
  - ALT or AST > 5 x ULN for > 2 weeks
  - ALT or AST > 3 x ULN and (total bilirubin > 2 x ULN OR INR > 1.5)
  - ALT or AST > 3 x ULN with the appearance of fatigue, nausea, vomiting, right upper quadrant pain or tenderness, fever, rash and/or eosinophilia (> 5%)

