#### 4.2 Inclusion Criteria

Patients must fulfill all of the following requirements to enter the study:

- 1. Signed informed consent obtained prior to initiation of any study-specific procedures and treatment;
- 2. Histologically or cytologically confirmed diagnosis of one of the following advanced or metastatic solid tumors for which standard therapy either does not exist or has proven ineffective, intolerable or inacceptable for the patient:
  - NUT midline carcinoma (ectopic expression of NUT protein as determined by IHC and/or detection of BRD-NUT gene translocation as determined by FISH);
  - Triple negative breast cancer defined according to ASCO recommendations (Hammond et al., 2010; Wolff et al., 2007);
  - Non-small cell lung cancer harboring a rearranged ALK gene/fusion protein (FISH or IHC) or KRAS mutation (as defined by any molecular analysis);
  - Castrate-resistant prostate cancer (CRPC);
  - Pancreatic ductal adenocarcinoma;
- 3. At least one measurable lesion as per RECIST version 1.1., except for CRPC patients who may be enrolled with objective evidence of disease as per Prostate Cancer Clinical Trials Working Group (PCWG2) criteria;
- 4. Age  $\geq$  18 years at the time of informed consent;
- 5. Life expectancy  $\geq$  3 months;
- 6. ECOG Performance Status (PS)  $\leq 1$ ;
- 7. Adequate bone marrow reserve, renal and liver function:
  - Absolute neutrophil count  $\geq 1.5 \times 10^9 / L$ ,
  - Platelet count  $\geq 150 \times 10^9 / L$ ,
  - Hemoglobin  $\geq 9$  g/dL (blood transfusion  $\leq 7$  days of screening not permitted),
  - Creatinine clearance ≥ 30 mL/min calculated according to the Cockroft and Gault formula or MDRD formula for patients aged > 65 years,
  - Alanine aminotransferase (ALT), aspartate aminotransferase (AST) < 3 x ULN, if alkaline phosphatase (ALP) > 2.5 X ULN, then liver fraction should be  $\le 2.5$  X ULN, and total bilirubin  $\le 1.25$  x ULN (in case of liver involvement, total bilirubin  $\le 2$  x ULN will be allowed),
  - Serum albumin  $\geq 2.0$  g/dL for NMC,  $\geq 3.0$  g/dL for NSCLC, CRPC, TNBC and pancreatic cancer
  - INR  $\leq 1.5$  or INR  $\leq 3$  for patients treated with antivitamin K;

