#### 4.3 Exclusion Criteria

The presence of any of the following criteria excludes a patient from participating in the study:

- 1. Inability to swallow oral medications or presence of a gastrointestinal disorder (e.g. malabsorption) deemed to jeopardize intestinal absorption of OTX015/MK-8628;
- 2. Persistent grade >1 clinically significant toxicities related to prior antineoplastic therapies (except for alopecia); stable sensory neuropathy ≤ grade 2 NCI-CTCAE v. 4.0 is accepted.
- 3. Known primary CNS malignancy or CNS involvement;
- 4. History of prior or concomitant malignancies (other than excised non-melanoma skin cancer or cured *in situ* cervical carcinoma) within 3 years of study entry;
- 5. Other serious illness or medical conditions, such as active infection, unresolved bowel obstruction, or psychiatric disorders;
- 6. Known HIV positivity;
- 7. Participation in another clinical trial or treatment with any investigational drug within 30 days prior to study entry;
- 8. Other concomitant anticancer treatment;
- 9. Concomitant therapy with strong CYP3A4 interfering drugs;
- 10. Current use of anticoagulants (e.g. warfarin, heparin) at therapeutic levels within 7 days prior to the first dose of OTX015/MK-8628. Low-dose (prophylactic) low molecular weight heparin (LMWH) is permitted;
- 11. Pregnant or breast-feeding patients, and men and women with childbearing potential not using effective contraception while on study treatment.

Any waiver of these inclusion and exclusion criteria should be exceptional and justified and must be approved by the investigator and the Sponsor on a case-by-case basis prior to enrolling the patient. This must be documented by both the Sponsor and the investigator.

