#### **Allowed**

- Supportive treatment of symptoms/AEs or standard treatment of concomitant conditions, including corticosteroids, aspirin, transfusion support, and antibiotics,
- Growth factors (G-CSF, EPO etc.) after cycle 1.
- For CRPC patients, maintenance treatment with ongoing androgen deprivation therapy with a gonadotropin releasing hormone (GnRH) analogue or antagonist is mandatory providing serum testosterone is < 50 ng/dL (<1.7 nmol/L), unless the patient had previous bilateral orchiectomy as part of his hormone therapy.
- Chemotherapy, hormone therapy or any other anticancer therapy or surgical intervention resection performed ≥ 3 weeks prior to study start (≥ 6 weeks for nitrosoureas or mitomycin C) or ≥ 3 half-lives for monoclonal antibodies or ≥ 5 half-lives for other non-cytotoxic agents (whichever is longer). Palliative radiation therapy (for analgesia) is authorized only if the irradiated field does not include target lesions.
- Bisphosphonates or denosumab given at stable doses for ≥ 4 weeks prior to study start. Bisphosphonates or denosumab are permitted from cycle 3.
- Prophylactic low-dose LMWH or antivitamin K (INR < 3); INR must be monitored in accordance with local institutional practices. Patients who develop venous thromboembolic events during study requiring therapeutic levels of LMWH must be closely monitored for their platelet counts.

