#### Not allowed

- Other concurrent investigational drugs, agents or devices or any other therapy for cancer treatment.
- Any drugs given with a prophylactic intent during the first cycle.

- Concurrent treatment with strong CYP3A4 interfering drugs/substances is not permitted. The concomitant use of other CYP3A4 interfering drugs or any CYP2A6 interfering drug is allowed provided a careful follow-up of laboratory results that may be influenced by the concomitant agent is performed (e.g. INR if the concomitant agent is an anticoagulant, blood cell counts if the concomitant drug is hematotoxic must be followed up more frequently than required by the protocol). A list is provided in Appendix 3, however since this list is not comprehensive, the investigator should use his/her medical judgment when a patient presents with a medication not on the list or call the Sponsor Medical Expert for clarification.
- Current use of anticoagulants (e.g. warfarin, heparin) at curative therapeutic levels within 7 days prior to the first dose of OTX015/MK-8628, with the exception of prophylactic low-dose LMWH or antivitamin K (INR < 3).

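### The liver DLT and discontinuation criterion uses an absolute INR > 1.5, while patients on antivitamin K may enter with INR up to 3 and eligibility for them is contradictory

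*Protocol*

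**What the plan says.** **Entry and co-medication.** Protocol section 4.2, inclusion criterion 7 (and the synopsis), requires INR ≤ 1.5, but allows INR ≤ 3 "for patients treated with antivitamin K". Section 6.2 lists as allowed "Prophylactic low-dose LMWH or antivitamin K (INR < 3); INR must be monitored in accordance with local institutional practices". Its list of prohibited treatments repeats that exemption from the anticoagulant ban. Section 4.3, exclusion criterion 10, excludes "Current use of anticoagulants (e.g. warfarin, heparin) at therapeutic levels within 7 days prior to the first dose of OTX015/MK-8628" and then exempts only low-dose LMWH.

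**Aminotransferases at entry.** Section 4.2 requires "Alanine aminotransferase (ALT), aspartate aminotransferase (AST) < 3 x ULN"; the synopsis has ≤ 3 x ULN.

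**Liver criterion.** Section 5.2.4 counts as a DLT "ALT or AST > 3 x ULN and (total bilirubin > 2 x ULN OR INR > 1.5" (closing bracket omitted). The same combination appears in the discontinuation list of section 5.3, in the event-of-clinical-interest list of section 8.9 and in the synopsis. The INR limit is absolute in all of them. The note under 5.2.4 does refer to baseline, but only for monitoring isolated bilirubin rises.

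**Filters.** Under 5.2.4 the investigator must consider a DLT related to study drug. Section 3.2 lets the Safety Monitoring Committee (SMC) disregard a DLT when determining the MTD, and the SMC charter in Appendix 4 has it validate DLTs. The list in 5.3 carries no relatedness wording. Section 5.2.7 has an override, with sponsor agreement, for discontinuation after long interruption or liver toxicity.

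**SAP.** Sections 2.4 to 2.6 define the primary endpoint as the number of patients with at least one cycle 1 DLT per regimen. They mention neither INR nor the liver criterion.

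**The concern.** There are two linked problems.

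First, eligibility is contradictory. A patient taking warfarin with an INR between 1.5 and 3 satisfies inclusion criterion 7 and section 6.2, but can be excluded by criterion 10, depending on how a site reads therapeutic level, which the protocol does not define. The limit itself also differs: ≤ 3 at entry, < 3 in section 6.2.

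Second, for such a patient the two-part liver criterion reduces to its aminotransferase part. It was written to need evidence of injury and evidence of impaired function together, but the functional part may be met before the first dose because of a permitted drug.

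At stake is the primary endpoint. In a 3+3 design one DLT in three patients requires expansion to six, and two mean that the dose level exceeds the MTD. The same bullet also ends treatment for the individual patient.

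**Working it through.** The documents give no figure for this point, so there is nothing to reproduce. The check has a textual part and an illustration.

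**Text, side by side**

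1. INR permitted at entry on antivitamin K: up to 3. INR part of the liver criterion: met above 1.5. Overlap: above 1.5 and up to 3.
2. ALT/AST at entry: < 3 x ULN (4.2) or ≤ 3 x ULN (synopsis). The aminotransferase part needs > 3 x ULN, so it is not met at baseline. A new rise on treatment is required.
3. In the overlap, the criterion is therefore completed by ALT/AST > 3 x ULN alone.
4. Other routes to a DLT in 5.2.4 already catch many such rises: ALT/AST > 8 x ULN; > 5 x ULN for > 2 weeks; > 3 x ULN with bilirubin > 2 x ULN; > 3 x ULN with listed symptoms such as fatigue or nausea; and any grade 3 or 4 laboratory abnormality lasting > 48 hours. The INR route adds only patients who meet none of these.

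**Illustration: how often**

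Assumptions, none stated in the documents:
- s = share of patients on antivitamin K, 3% to 10%, all taken to have baseline INR > 1.5.
- a = chance that such a patient has ALT/AST > 3 x ULN in cycle 1 without meeting another DLT criterion, 5% to 20%.

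Per-patient rate f = s × a, before attribution or SMC review:
- low: 0.03 × 0.05 = 0.0015
- high: 0.10 × 0.20 = 0.02

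Chance of at least one such DLT in n patients = 1 − (1 − f)^n. The Protocol's maximum per regimen is 4 dose levels × 6 = 24.

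| n | f = 0.0015 | f = 0.02 |
|---|---|---|
| 6 | 0.9% | 11.4% |
| 24 | 3.5% | 38.4% |

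**Illustration: average effect on escalation**

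Under the rule in 5.2.3, with per-patient DLT rate p, P(escalate) = (1−p)³ + 3p(1−p)² × (1−p)³. True DLT rates of 10% and 20% are also assumptions.

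- p = 0.10: 0.7290 + 0.1771 = 90.6%
- p = 0.20: 0.5120 + 0.1966 = 70.9%

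Adding the extra DLTs replaces p by p + (1−p)f:

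- p = 0.10: 90.4% (f = 0.0015) to 87.5% (f = 0.02, rate 0.10 + 0.90 × 0.02 = 0.118)
- p = 0.20: 70.6% to 67.4% (f = 0.02, rate 0.20 + 0.80 × 0.02 = 0.216)

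**Illustration: effect of one counted case**

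If one of the first three patients has such a DLT and it counts, escalation needs no DLT in the other two or in the next three: P(escalate) = (1−p)² × (1−p)³ = (1−p)⁵.

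- p = 0.10: 0.9⁵ = 59.0%, against 90.6%
- p = 0.20: 0.8⁵ = 32.8%, against 70.9%

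**The case against.** The strongest reply is that the plan already has people to deal with this. The investigator must judge the event related, the SMC validates DLTs and may disregard one for the MTD, and Appendix 5 requires a concomitant-medication history and a search for other causes. That stands as a reason why the effect on the MTD may be filtered. It does not settle the point: no rule says how to treat this case, and an investigator may properly call the ALT/AST rise related when the INR is not. In 5.3 relatedness is not mentioned, and its perceived-benefit exception covers long interruption and DLT recurrence, not the liver bullets. The override in 5.2.7 mentions liver toxicity, but how it fits with 5.3 is unclear.

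A second reply is that section 6.2 shows the intended reading of exclusion criterion 10, which merely omits a phrase. That is plausible. If criterion 10 is instead applied strictly, few such patients enrol and the DLT problem shrinks. Either way, sites need one reading.

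A third reply is that an absolute INR limit may be a deliberate caution. Factor VII decreases possibly or probably related to the drug are tabulated in section 1.3.3.2 (Tables 6 and 7), so a rise in INR on treatment can be a genuine drug signal. This stands. A reader might infer that INR > 1.5 in these patients reflects only the anticoagulant; the documents do not support that. The absolute limit cannot separate the two causes, which is a reason to list the baseline value rather than to dismiss the event.

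**Conclusion.** The contradiction is real and appears in both the synopsis and the body of the protocol. Followed as written, the plan can count a DLT, or stop treatment, on a criterion whose INR half was met at entry.

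Its average size is small: under the assumed inputs, P(escalate) falls by about 0.2 to 3.1 points at a true DLT rate of 10% (90.6% to 90.4-87.5%) and by about 0.3 to 3.5 points at 20% (70.9% to 70.6-67.4%), before attribution or SMC review. What makes it worth fixing is the weight of one counted case in a cohort of three. All these figures rest on assumed antivitamin K use, aminotransferase rates and true DLT rates.

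Three stronger readings are tempting but not supported:

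- **That every antivitamin K patient meets half the criterion at baseline.** Only those admitted with INR above 1.5 do, and nothing is triggered without a new ALT/AST rise.
- **That the chance of enrolling an antivitamin K user measures the problem.** At 3-10% use, the chance of at least one is 1 − (1−s)^n = 17-47% in 6 patients and 52-92% in 24. That is the chance that such a patient is present, not of a false DLT.
- **That the aminotransferase threshold for these patients drops from 8 x to 3 x ULN.** The other routes in 5.2.4 already count many events between those values.

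Nor do the documents show that the MTD will be biased downward, since SMC discretion may remove such cases.

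**What to change.** **Protocol.** Reconcile inclusion criterion 7, exclusion criterion 10, section 6.2 and the liver criterion in 5.2.4, 5.3 and 8.9, with their synopsis counterparts. The text should give one answer on whether antivitamin K patients are eligible and at what INR, and should say how the INR part applies to a patient admitted with INR above 1.5. Clarify how 5.2.7 and 5.3 fit together for liver toxicity. Any clinical threshold or stopping rule is for the sponsor to set.

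**SAP.** In sections 2.4 and 2.6, flag any DLT that qualifies only through ALT/AST > 3 x ULN plus an INR within the range permitted at entry for antivitamin K patients. List baseline and on-treatment INR and Factor VII for each; section 7 already collects both. Report the primary endpoint with and without the flagged cases.

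**Cost.** Wording changes in the protocol, and one sentence, one listing and one extra count in the SAP. No additional patients or assessments are needed. The SAP step remains usable for cohorts that have already completed escalation.

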#### Other

• Treatment delay > 2 weeks or dose reduction requirement for initiating cycle 2.

\*\*Note: All patients with these liver test abnormalities should be monitored weekly until all abnormalities return to normal or to the baseline state. For patients with isolated total bilirubin increases >2 x ULN or 2 x baseline (if elevated at baseline), monitoring should be every 2 weeks until bilirubin returns to normal or to the baseline state. Drug induced liver injury (DILI) may develop or progress even after the causative drug has been stopped. Results should be recorded in the CRF and in the database. See guidelines on the handling of these events (potential Hy's law cases)(Appendix 5).

DLTs must be reported immediately to the Sponsor using a Serious Adverse Event Report Form (SAERF) with the reason for seriousness "other important medical event" if there is no other reason for seriousness.

#### 5.2.5 Maximum Tolerated Dose

The MTD (recommended phase II dose) is defined as the dose immediately preceding the DL at which DLTs are observed in  $\geq 2$  out of 3 to 6 patients, i.e., the DL at which 0 of 3 patients or  $\leq 1$  of 6 patients experience DLT.

The MTD will be determined in each of the two regimens evaluated.

#### 5.2.6 Expansion Cohort

Once the MTD is established for each regimen with at least 3 patients having received at least 2 evaluable cycles of study drug, the study will be extended with the inclusion of 10 evaluable patients per indication at the MTD. The regimen used in each expansion cohort (i.e., each indication) will be decided by the SMC.

#### 5.2.7 Dose Adaptation

OTX015/MK-8628 will be interrupted until recovery to  $\leq$  grade 1 or baseline value in the event of any of the following toxicities:

# Hematologic toxicity

- Any grade 4 hematologic toxicity or febrile neutropenia
- Grade 3 neutropenia with infection
- Grade 3 thrombocytopenia with bleeding or lasting > 7 days

# Non-hematologic toxicity

- Any grade 3 or 4 non-hematologic toxicity (regardless of duration) unless it was not optimally managed with supportive care (e.g. grade 3 vomiting not adequately treated according to antiemetic standard of care).
- Any grade 3 or 4 laboratory abnormality, with or without symptoms, lasting > 48 hours.
- Any intolerable grade 2 non-hematologic toxicity resulting in study drug discontinuation or delay > 7 days with or without dose reduction.

After recovery from toxicity, the dose will be resumed as follows and detailed in Table 11:

- For Regimen 1, the continuous schedule will be initially modified to a discontinuous schedule, then with a dose reduction for the second modification.
- For Regimen 2, two consecutive dose reductions may be implemented.

Dose / Schedule Modifications: Regimen 1 2nd Modification **Initial OTX015 Dose** 1st Modification 80 mg QD continuously 80 mg QD, 60 mg QD, 2 weeks ON/1 week OFF, q3w 2 weeks ON/1 week OFF, q3w 100 mg QD continuously 100 mg QD, 80 mg OD. 2 weeks ON/1 week OFF, q3w 2 weeks ON/1 week OFF, q3w 120 mg QD continuously 120 mg QD, 100 mg QD, 2 weeks ON/1 week OFF, q3w 2 weeks ON/1 week OFF, q3w 160 mg QD continuously 120 mg OD, 160 mg OD, 2 weeks ON/1 week OFF, q3w 2 weeks ON/1 week OFF, q3w

Table 11: OTX015/MK-8628 Dose / Schedule Modifications

Dose / Schedule Modifications: Regimen 2 **Initial OTX015 Dose** 1st Modification 2nd Modification 100 mg QD, Days 1-7, q3w 80 QD, Days 1-7, q3w 60 QD, Days 1-7, q3w 120 mg QD, Days 1-7, q3w 80 QD, Days 1-7, q3w 100 mg QD, Days 1-7, q3w 160 mg QD, Days 1-7, q3w 120 mg QD, Days 1-7, q3w 100 mg QD, Days 1-7, q3w

No more than two dose reductions (or schedule modifications) should be implemented unless the investigator thinks it in the patient's best interests to pursue study treatment with further dose reduction (additional dose reduction by one dose level), with the Sponsor's agreement.

120 mg QD, Days 1-7, q3w

160 QD, Days 1-7 q3w

Dosing interruption for > 2 weeks due to toxicity or liver toxicity (see Section 5.3 for details) will lead to definitive study treatment discontinuation, unless the investigator thinks it in the patient's best interests to pursue study treatment, with the Sponsor's agreement.

